10.3 Statistical Methods

We will begin all analyses with descriptive summary statistics and graphical displays of all variables. Primary analyses will utilize Poisson mixed-effects models for the provider-level CW compliance rate, with treatment group as the primary fixed effect of interest and practice as a random effect to accommodate clustering of providers within practices. We will assess whether negative binomial regression is warranted because of overdispersion. We will also explore non-parametric methods such as quantile regression and other rank-based approaches. Although randomization should obviate the need for any additional adjustment, we will explore whether adjustment for provider-level characteristics, such as demographics, panel size, or insurance mix, is necessary.

11 Source Documents and Access to Source Data/Documents

Source data is all information, original records of clinical findings, observations, or other activities in a study necessary for the reconstruction and evaluation of the study. Source data are contained in source documents. Examples of these original documents, and data records include: hospital records, clinical and office charts, laboratory notes, memoranda, subjects' diaries or evaluation checklists, pharmacy dispensing records, recorded data from automated instruments, copies or transcriptions certified after verification as being accurate and complete, microfiches, photographic negatives, microfilm or magnetic media, x-rays, subject files, and records kept at the pharmacy, at the laboratories, and at medicotechnical departments involved in the study.

The EPIC electronic health record is the primary data collection instrument for the study. Study-specific case report forms will not be used.

Access to study records will be limited to IRB-approved members of the study team. The investigator will permit study-related monitoring, audits, and inspections by the IRB/EC, the sponsor, government regulatory bodies, and University compliance and quality assurance groups of all study related documents (e.g., source documents, regulatory documents, data collection instruments, study data etc.). The investigator will ensure the capability for inspections of applicable study-related facilities (e.g., pharmacy, diagnostic laboratory, etc.).

12 Ethics/Protection of Human Subjects

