Brief Summary	This RCT will test a new electronic health record module to improve guideline-compliant care of older adults with diabetes. The module incorporates effective behavioral economics (BE) principles to improve the degree to which care of older adults is compliant with Choosing Wisely (CW) guidelines; this generally involves less aggressive targets for HbA1c, and reductions of medications other than metformin. The implementation of the module is triggered by patient scheduling and medication prescribing in EPIC. The BE principles include suggesting alternatives to medications, requiring justification, setting of appropriate default order sets, and incorporation of anchoring and checklists to guide behavior.
Objectives	Primary objective: to test a customized EHR toolkit that applies BE insights to promote appropriate diabetes care in older adults based on the American Geriatric Society's Choosing Wisely guideline, and to assess the acceptability of the resulting module. Secondary objective: to assess the "usability" of the proposed BE-EHR module in clinical practice.
Methodology	Cluster-randomized controlled trial
Endpoints	Primary endpoint: Choosing Wisely guideline compliance Secondary endpoint: medication prescribing patterns
Study Duration	Eighteen months
Participant Duration	Eighteen months
Population	Patients age 75 or older with diabetes
Study Sites	One single site at NYULH consisting of approximately 70 outpatient practices in primary care, geriatrics, or endocrinology
Number of participants	Approximately 5000
Statistical Analysis	We will begin all analyses with descriptive summary statistics and graphical displays of all variables. Primary analyses will utilize Poisson mixed-effects models for the provider-level CW compliance rate, with treatment group as the primary fixed effect of interest and practice as a random effect to accommodate clustering of providers within practices. We will assess whether negative binomial regression is warranted because of overdispersion. We will also explore non-parametric methods such as quantile regression and other rank-based approaches. Although randomization should obviate the need for any additional adjustment, we will explore whether adjustment for provider-level characteristics, such as demographics, panel size, or insurance mix, is necessary.

Schematic of Study Design

Prior to Enrollment	Identify ~70 NYULH clinics to participate
	\int

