4.3 Randomization

There are currently 81 primary care practices in our FGP. Practice sites will be randomized using variable block sizes of 4 and 6 to ensure balance, with an even randomization ratio that will result in half of the sites randomized to the BE-EHR module activation (BE-EHR) and half randomized to usual care (UC). Randomization will be stratified by practice size (<= 100 patients vs > 100 patients over 75 with diabetes) to ensure balance. [name] will request that the randomization scheme be generated by one of her faculty or staff members in the Division of Biostatistics who is unaffiliated with the project, in order to maintain blinding of assignment by the study team.

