5.6 Total Number of Participants and Sites

This is a single site study involving approximately 70 NYULH outpatient clinics serving a total of approximately 5000 participants.

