6.2 Enrollment/Baseline

Not applicable.

CONFIDENTIAL

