10.2 Sample Size Determination

Our preliminary data indicate that approximately 30-40% of eligible patients have care that is CWcompliant. We wish to be able to detect an increase in the rate of CW-compliant care of ten percentage points or more. We conservatively estimate an ICC (intra-class correlation coefficient, a measure of the degree of additional correlation among providers within the same practice) of 0.05; with an average of four providers per practice site at 70 sites, this leads to a design effect of 1.15. The sample of 280 providers becomes an effective sample size of 244, providing approximately 87% power to detect a difference of ten percentage points between the study arms.

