12.2 Institutional Review Board

The protocol for study i19-01464, request for waiver of informed consent, and request for waiver of HIPAA authorization will be submitted to the IRB for review and approval. Approval of the protocol, the waiver of consent, and the waiver of HIPAA authorization must be obtained before any participant is enrolled. Any amendment to the protocol will require review and approval by the IRB before the changes are implemented to the study.

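### Practices are randomised within size strata, but the primary model has no stratum term, so its standard error is somewhat too large if compliance varies with practice size

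*Combined protocol and SAP*

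**What the plan says.** On the design, Section 4.3 states "Randomization will be stratified by practice size", with two levels: at most 100, or more than 100, older patients with diabetes. It uses blocks of 4 and 6 and equal allocation. Section 7.1 repeats this.

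On the analysis, Section 10.3 and the Statistical Analysis row of the Protocol Summary carry the same text: "Primary analyses will utilize Poisson mixed-effects models for the provider-level CW compliance rate". In both places the terms of that model are then set out: "with treatment group as the primary fixed effect of interest and practice as a random effect to accommodate clustering of providers within practices". Neither place mentions the stratum. The only provision for covariates is exploratory: "Although randomization should obviate the need for any additional adjustment, we will explore whether adjustment for provider-level characteristics" is needed, with demographics, panel size and insurance mix as examples. These belong to the provider, so a provider's panel size is not the practice-size stratum.

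On size, Section 10.2 assumes an ICC of 0.05 and, "with an average of four providers per practice site at 70 sites, this leads to a design effect of 1.15", an effective sample of 244 providers and about 87% power for a ten-point difference.

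**The concern.** Stratified blocks force the arms to be balanced on practice size, so any difference in compliance between large and small practices largely cancels out of the treatment contrast. A model without the stratum leaves that difference in the practice variance and charges it to the standard error. The estimate is then more precise than the analysis reports.

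The argument that randomisation makes adjustment unnecessary is sound as regards bias. It does not cover the standard error when the factor was itself used to constrain the randomisation. Because adjustment is left to exploration, with no rule for when it is needed, adding the stratum later could be challenged as data-driven. At stake is a slightly wide interval and a little lost power, not a wrong conclusion.

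**Working it through.** **Inputs from the plan (Section 10.2).** ICC 0.05; four providers at each of 70 practices (280 in all); difference 0.10; power about 87%.

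**Assumed, because not stated.** Two-sided alpha of 0.05, and a between-provider SD of 0.25 for the compliance rate. Let f be the share of between-practice variance explained by the stratum. The documents give no figure for f, so a range is used.

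**1. The plan's own figures.** Design effect 1 + (4 − 1) × 0.05 = 1.15, and 280/1.15 = 243.5; both reproduce. SE = 0.25 × √(4/243.5) = 0.03204. A two-sided t test then has 87.5% power, in line with the stated 87%. This agreement depends on the assumed SD.

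**2. Ceiling on the gain.** The between-practice share of the variance of a practice mean is 0.05/(0.05 + 0.95/4) = 0.174. Removing the stratum component multiplies the variance by 1 − 0.174f, so at most 17.4% can be removed.

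**3. What f means in compliance terms.** For equal strata the gap is 2 × √(f × 0.05 × 0.25²). For f = 0.10 / 0.25 / 0.50 / 1.00 this is 3.5 / 5.6 / 7.9 / 11.2 percentage points.

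**4. Reported standard error.** Including the stratum lowers it from 0.03204 to 0.03176 / 0.03134 / 0.03062 / 0.02912, a fall of 0.9 / 2.2 / 4.5 / 9.1%. The 95% half-width goes from 6.3 to 6.3 / 6.2 / 6.0 / 5.7 points. Set against a fixed 87.5%, power becomes 88.0 / 88.8 / 90.2 / 92.8%.

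**5. Why that power comparison overstates the gain.** Stratified blocks reduce the true spread of the estimate whether or not the model includes the stratum, so power with the stratum omitted also rises with f. Take f = 0.50 with practice-level critical values (1.9955 on 68 df, 1.9960 on 67) and a normal approximation:

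- omitted: (0.10 − 1.9955 × 0.03204)/0.03062 = 1.178, power 88.1%;
- included: 0.10/0.03062 − 1.9960 = 1.270, power 89.8%.

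The like-for-like gain is 1.7 points, not 90.2 − 87.5 = 2.7. In the same way, type I error with the stratum omitted uses an effective critical value of 1.9955/√(1 − 0.174f). It comes to 4.8 / 4.5 / 4.1 / 3.2% across the four values of f.

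**6. Like-for-like simulation.** 20,000 trials per setting; blocks of 4 and 6 within stratum; 35 practices per stratum; least squares on practice means; total ICC held at 0.05.

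| f | gap (points) | power omitted / included (%) | type I error omitted / included (%) |
|---|---|---|---|
| 0 | 0 | 86.5 / 86.4 | 4.9 / 4.9 |
| 0.10 | 3.5 | 86.8 / 87.2 | 4.8 / 4.9 |
| 0.25 | 5.6 | 87.4 / 88.2 | 4.4 / 4.9 |
| 0.50 | 7.9 | 87.7 / 89.5 | 4.2 / 5.1 |
| 1.00 | 11.2 | 89.4 / 92.7 | 3.1 / 5.0 |

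Monte Carlo standard error is about 0.24 points for power and 0.15 for type I error.

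**7. Unequal strata.** Section 5.6 gives "approximately 70 NYULH outpatient clinics serving a total of approximately 5000 participants", so the mean is 5000/70 = 71 patients and the larger-practice stratum may be the smaller group. With an assumed 14 large and 56 small practices, the power gains are 0.3 / 0.8 / 1.9 / 3.5 points, and type I error with the stratum omitted is 4.9 / 4.5 / 4.1 / 3.2%. The same f then means gaps of 4.4 / 7.0 / 9.9 / 14.0 points.

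**8. Independent check of the mechanism.** A second simulation (8,000 runs, 30% large practices, SD 0.253, f = 0.50) gave a mean reported SE of 0.0323 with the stratum omitted, against an actual spread of 0.0307. With the stratum included the figures were 0.0309 and 0.0306. Power was 86.7% against 88.7%.

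**The case against.** The strongest reply is that stratification has already delivered the precision. Step 8 bears this out: the spread of the estimate is almost the same either way (0.0307 and 0.0306). What the stratum term improves is the reported standard error, which otherwise makes a valid test mildly conservative. That stands, as does the point that the power series in step 4 overstates the gain. The conclusion here rests on the like-for-like figures in steps 5 to 7.

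It is also true that no document shows compliance to differ by practice size, so the gain could be zero, and that f = 1.00 is a limit rather than a scenario. Both stand. They limit the size of the point but do not answer it, because including an irrelevant stratum changes power by no more than about 0.1 point.

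Finally, Section 10.3 calls treatment the primary fixed effect of interest, which does not strictly exclude other fixed effects, and it allows for exploring adjustment. But it names no other fixed effect, and it presents adjustment as something randomisation should make unnecessary. An analyst following the text would fit treatment alone.

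**Conclusion.** The point holds as a small, recommended refinement. The planned analysis is valid: no bias, no inflation of type I error, and no conclusion made wrong. If practice size is related to compliance, the reported interval is wider than the stratified design supports. The like-for-like power gain from including the stratum is under 1 point for gaps up to about 6 points between equal strata, about 2 points for a gap near 8, and about 3.5 points at the ceiling.

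These sizes rest on the assumed SD of 0.25, two-sided alpha of 0.05, the plan's ICC of 0.05 and four providers per practice. They are linear approximations on practice means; the Poisson mixed model itself was not fitted. A larger true ICC would raise the possible gain and a smaller one would lower it. That the stratum is missing from the model is certain; how much this matters is not known from the documents.

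**What to change.** Before outcome data are seen, restate the primary model in Section 10.3 and the Protocol Summary as fixed effects for arm and practice-size stratum (the two levels used to randomise) plus a practice random intercept. Label every other adjusted model as secondary.

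This needs no new data, patients or practices, because the stratum must be known for each practice before it is randomised. It uses one practice-level degree of freedom (68 to 67). It changes protocol text, and Section 12.2 states "Any amendment to the protocol will require review and approval by the IRB before the changes are implemented to the study", so an amendment is required.

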12.1 Ethical Standard

The investigator will ensure that this study is conducted in full conformity with Regulations for the Protection of Human Subjects of Research codified in 45 CFR Part 46.

12.2 Institutional Review Board

The protocol for study i19-01464, request for waiver of informed consent, and request for waiver of HIPAA authorization will be submitted to the IRB for review and approval. Approval of the protocol, the waiver of consent, and the waiver of HIPAA authorization must be obtained before any participant is enrolled. Any amendment to the protocol will require review and approval by the IRB before the changes are implemented to the study.

12.3 Informed Consent Process

We will obtain a waiver of informed consent and a waiver of HIPAA authorization for patients seen in the participating clinics to acknowledge their participation at a clinic level. The risks to subjects are exactly equivalent to the risks experienced in the standard setting of patient care. The new module to be activated in EPIC relates only to guidance for physician decision-making regarding diabetes care, and has no impact on disclosure or treatment of PHI. Subjects will receive care from their providers in the usual way. The only difference is the interface with the electronic health record that is used by the physician during the course of the patient encounter. The autonomy of the provider to make decisions about patient care will not be affected. It is impracticable to obtain consent from patients for receipt of standard medical care by their usual providers. It is unclear what they would be providing consent for, since they will receive care as usual from their providers. Patients will not be provided with additional information. They will be treated as usual by their providers and the providers' experience with the module is irrelevant to their patient experience.

12.3.1 Consent/Assent and Other Informational Documents Provided to Participants

Not applicable.

12.3.2 Consent Procedures and Documentation

Not applicable.

12.3.3 Research Use of Stored Human Samples, Specimens, or Data

No human samples or specimens will be collected.

- Intended Use: Data collected under this protocol may be used to study the effectiveness of the module.
- Tracking: Data will be tracked using Epic reports generated by study team members.
 - Disposition at the completion of the study. Data will be retained in de-identified electronic form on secure, password-protected digital storage media at the NYU central site, under the supervision of [name], for use by other researchers including those outside of the study.

12.4 Future Use of Stored Human Samples, Specimens, or Data

No specimens will be collected.

Data collected for this study will be analyzed and stored at NYU Langone Health. After the study is completed, the de-identified, archived data will be transmitted to and stored at the NYU central site, under the supervision of [name], for use by other researchers including those outside of the study.

When the study is completed, access to study data will be provided through the study database.

13 Data Handling and Record Keeping

13.1 Data Collection and Management Responsibilities

Data collection is the responsibility of the study staff at NYULH under the supervision of [name]. The investigator is responsible for ensuring the accuracy, completeness, legibility, and timeliness of the data reported.

13.2 Study Records Retention

Study documents and data will be retained for the longer of 3 years after close out or 5 years after final reporting/publication. These documents should be retained for a longer period, however, if required by local regulations. No records will be destroyed without the written consent of the sponsor, if applicable. It is the responsibility of the sponsor to inform the investigator when these documents no longer need to be retained.

13.3 Protocol Deviations

A protocol deviation is any noncompliance with the study protocol or MOP requirements. The noncompliance may be either on the part of the participant, the investigator, or the study site staff. As a result of deviations, corrective actions are to be developed by the site and implemented promptly.

It is the responsibility of the site to use continuous vigilance to identify and report deviations within five working days of identification of the protocol deviation. All deviations must be addressed in study source documents and reported to the designated Safety Officer. Protocol deviations must be reported to the local IRB per their guidelines. The site Pl/study staff is responsible for knowing and adhering to their IRB requirements. Further details about the handling of protocol deviations will be included in the MOP.

13.4 Publication and Data Sharing Policy

This study will comply with the NIH Public Access Policy, which ensures that the public has access to the published results of NIH funded research. It requires scientists to submit final peer-reviewed journal manuscripts that arise from NIH funds to the digital archive PubMed Central upon acceptance for publication.

14 Study Finances

14.1 Funding Source

This study is financed through a grant from the National Institutes of Health – National Institute on Aging.

14.2 Costs to the Participant

There are no costs to participants in this study.

14.3 Participant Reimbursements or Payments

There are no participant reimbursements or payments.

CONFIDENTIAL

15 Study Administration

